9.7.1.9 Efficacy Analyses

9.7.1.9.1 Primary Analyses

The primary null hypothesis was that restoration of level of consciousness (defined as a return to GCS scores ≥ 13) of subjects with probable or definitive EHS was not different for subjects treated with SOC plus adjuvant Ryanodex therapy compared to subjects treated with SOC only. [REDACTED]

[REDACTED], the primary endpoint was the cumulative incidence of subjects achieving a GCS score ≥ 13 at or prior to 90 minutes post-randomization in the ITT Analysis Set.

The number and percentage of subjects who achieved a GCS score ≥ 13 at or prior to 90 minutes post-randomization were presented by treatment arm. A 2-sided 95% Wilson CI for each treatment group proportion and a 2-sided 95% Newcombe CI for the treatment difference were calculated. [REDACTED]

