2.0 SYNOPSIS

Name of Sponsor/Company: Eagle Pharmaceuticals, Inc.	Individual Study Table	(For National Authority Use only)
Name of Finished Product: Ryanodex® (dantrolene sodium) for injectable suspension		
Name of Active Ingredient: Dantrolene sodium		
Title of Study: Phase 2, Single-Site, Open-Label, Randomized, 2-Arm Parallel Study to Assess the Efficacy and Safety of Ryanodex® (EGL-4104) as Adjuvant Treatment in Subjects With Exertional Heat Stroke (EHS)		
Investigators: [REDACTED]		
Study Centers: The study was conducted at a single site with 3 additional satellite site locations in the region of Mekkah, Saudi Arabia, during the 2015 Hajj pilgrimage.		
Publication (Reference): None		
Study Period: 22 September 2015 (First Subject Enrolled) - 27 September 2015 (Last Subject Completed Treatment)	Phase of Development: 2	
Objectives: Primary : To evaluate the efficacy of Ryanodex for the treatment of EHS, administered as adjunctive treatment to current standard of care (SOC). Secondary : To evaluate the safety and tolerability of Ryanodex for the treatment of EHS by comparing the treatment groups for the incidence of treatment-emergent adverse events (TEAEs), physical and neurological examination findings, clinical laboratory test results, and vital signs.		
Methodology: [REDACTED]		

Name of Sponsor/Company:	Individual Study Table	(For National Authority Use only)
Eagle Pharmaceuticals, Inc.		
Name of Finished Product:		
Ryanodex® (dantrolene sodium) for injectable suspension		
Name of Active Ingredient:		
Dantrolene sodium		

Treatment Groups:

Upon admission to the emergency medical facility and following assessment of study inclusion and exclusion criteria, eligible subjects with probable or definitive EHS were randomized in a 1:1 ratio to one of the following treatment groups:

- Group A: Ryanodex, in addition to immediate implementation of SOC (body cooling and supportive measures)
- Group B: SOC only (body cooling and supportive measures) implemented immediately

Subjects randomized to Group A received an initial dose of Ryanodex (study drug) of 2 mg/kg administered as an IV bolus, in addition to SOC. If the subject did not show adequate clinical response between 30 and 90 minutes after the initial dose, a single repeat dosing of 2 mg/kg of study drug could be administered between 30 and 90 minutes following the initial dose.

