Subjects who had received up to two 2-mg/kg (up to 4 mg/kg) IV doses of Ryanodex (Group A) during the Treatment Phase of the study could receive additional treatment with Ryanodex at a dose of 1 mg/kg as an IV bolus starting at 90 minutes following the initial dose and continuing every 6 hours for up to 24 hours under the following conditions:

1. If the subject had not achieved an adequate response (defined as rectal temperature $\leq 38.0^{\circ}\text{C}$ and Glasgow Coma Scale (GCS) score ≥ 13); or,
2. If the subject had achieved an adequate response (defined as rectal temperature $\leq 38.0^{\circ}\text{C}$ and GCS ≥ 13) but the symptoms began to reappear

Clinical assessments and symptoms leading to additional doses of study drug were to be clearly recorded. The total administered dose of Ryanodex in a [REDACTED] period was not to exceed [REDACTED]

Stopping the study drug:

If [REDACTED]

The study protocol included three phases (Screening/Randomization, Treatment Phase, and Follow-up

Name of Sponsor/Company: Eagle Pharmaceuticals, Inc.	Individual Study Table	(For National Authority Use only)
Name of Finished Product: Ryanodex® (dantrolene sodium) for injectable suspension		
Name of Active Ingredient: Dantrolene sodium Phase), plus a follow-up contact by telephone at approximately [REDACTED] days after the subject's discharge from the study.		
Number of Subjects (Planned and Analyzed): A total of 100 subjects (50 per arm) were initially planned to be randomized in the study. Due to unforeseen tragic events impacting the location of the study and enrollment plans, 40 subjects were screened to participate, and 34 subjects were randomized (6 subjects were screen failures). A total of 34 subjects were analyzed for efficacy and safety.		
Diagnosis and Main Criteria for Inclusion: Male or non-pregnant female subjects were entered into this study if they were diagnosed with probable or definitive EHS as evidenced by all of the following: 
 • A core body temperature obtained rectally of $\geq 40.0^{\circ}\text{C}$ (104.0°F) • In the judgment of the Investigator, the subject was likely 18 years of age or older, and not older than 45 years of age • Recent history or suspected recent history (prior 24 hours) of performing intense physical activity (exertional activity) • The subject had impaired consciousness level as evidenced by a GCS score < 13 • The subject had tachycardia (heart rate ≥ 100 beats per minute [bpm]). 		

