
 • A greater proportion of subjects treated with SOC and Ryanodex exhibited a clinically meaningful improvement in their neurological functioning (GCS ≥ 13) within 90 minutes (29.4%) and within 24 hours post-randomization (47.1%), compared to SOC only-treated subjects (11.8% and 23.5%, respectively) (ITT Analysis Set). • A greater proportion of subjects treated with SOC and Ryanodex achieved a clinically meaningful improvement (GCS score ≥ 13) in their neurological functioning as early as 45 minutes post-randomization compared to subjects treated with SOC only, and that difference in favor of the SOC and Ryanodex group remained unchanged at the end of the Treatment Phase (2 hours post-randomization) (ITT and mITT Analysis Sets). • The odds of achieving a GCS score ≥ 13 within 90 minutes post-randomization was about 3 times greater for subjects in the SOC and Ryanodex group than for subjects who received SOC only, and remained almost unchanged at or prior to 24 hours post-randomization (ITT Analysis Set). • Among fully evaluable subjects at Baseline, the odds of achieving a GCS score ≥ 13 within 90 minutes post-randomization was about 6 times greater in the SOC and Ryanodex group than for subjects who received SOC only (mITT Analysis Set). • Among fully evaluable subjects at Baseline, the mean change from Baseline in GCS score was higher in the SOC and Ryanodex group (3.1; $p=0.017$) compared with the SOC only group (1.1; $p=0.179$); the mean percent change from Baseline in GCS score was also higher in the SOC and Ryanodex group (55.6%; $p=0.073$) compared with the SOC only group (20.2%; $p=0.212$). In both cases, the within-group p-value clearly favors the SOC and Ryanodex group, compared with the SOC only group (mITT Analysis Set). • The proportion of subjects who achieved complete normalization in their level of consciousness (GCS score = 15) was greatest at 24 hours post-randomization and was greatest in the SOC and Ryanodex group (41.2%) than in the SOC only group (23.5%) (ITT Analysis Set). • Duration of SOC was substantially shorter in the SOC and Ryanodex group compared to the SOC only group (ITT Analysis Set). • The time to reach first rectal temperature $\leq 38^{\circ}\text{C}$ was similar in both treatment groups (ITT Analysis Set). • The median time to reach first rectal temperature $\leq 38^{\circ}\text{C}$ was shorter in the SOC and Ryanodex group (90.0 minutes) than in the SOC only group (103.0 minutes). In addition, the time at which at least 75% of the subjects had first rectal temperature $\leq 38^{\circ}\text{C}$ was also shorter in the SOC and Ryanodex group (125.0 minutes) than in the SOC only group (195.0 minutes) (mITT Analysis Set). • Overall mean cooling rates were similar in both treatment groups (ITT and mITT Analysis Sets). 
Subjects treated with Ryanodex in addition to SOC, exhibited greater clinically meaningful improvement in their neurological functioning compared to SOC only-treated subjects. The observed incremental improvement in neurologic functioning constitutes a clinically relevant benefit, known to be associated
		

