
Name of Sponsor/Company: Eagle Pharmaceuticals, Inc.	Individual Study Table	(For National Authority Use only)
Name of Finished Product: Ryanodex® (dantrolene sodium) for injectable suspension		
Name of Active Ingredient: Dantrolene sodium		
with lower risk of EHS-related complications, and decreased long-term morbidity and mortality.		

Safety Results:
 
 • Ryanodex was safe and well-tolerated by subjects in the SOC and Ryanodex group. • No new and/or unexpected safety signals were detected. • The overall incidence of TEAEs was similar in both groups. • No treatment-related TEAEs were reported. • No subjects withdrew due to TEAEs. • There were no clinically meaningful differences in laboratory abnormalities between the two treatment groups. • There were no clinically meaningful differences in vital signs, ECGs, ETCO₂, or oxygen saturation between the two treatment groups. • The safety profile of Ryanodex in this study population was consistent with the known and well-characterized safety profile in the currently approved indications. 		

Conclusion:
 
Overall, Ryanodex administered to EHS subjects was safe and well tolerated. The safety profile of Ryanodex in this severely ill population was consistent with its known and well-characterized safety profile in the currently approved indications.
 
Subjects treated with Ryanodex, in addition to SOC, exhibited greater clinically meaningful improvement in their neurological functioning compared to SOC only-treated subjects. The observed incremental improvement in neurologic functioning constitutes a clinically relevant benefit, known to be associated with lower risk of EHS-related complications, and decreased long-term morbidity and mortality.
 
The results of the study provide clinical evidence of the therapeutic benefit that Ryanodex may deliver to patients with EHS.

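### The Conclusion states a neurological benefit as fact, without the open-label design or an interval, on a primary ITT difference of three subjects whose 95% interval includes zero

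*Combined protocol and SAP*

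**What the plan says.** The title in the Synopsis describes a "Phase 2, Single-Site, Open-Label, Randomized, 2-Arm Parallel Study". Under Treatment Groups, "eligible subjects with probable or definitive EHS were randomized in a 1:1 ratio". Under Number of Subjects, 100 were planned, 34 were randomized, and "A total of 34 subjects were analyzed for efficacy and safety".

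SAP section 9.7.1.9.1 states that "the primary endpoint was the cumulative incidence of subjects achieving a GCS score ≥ 13 at or prior to 90 minutes post-randomization" in the ITT set. It specifies Wilson 95% intervals for each arm and a Newcombe 95% interval for the difference. SAP section 9.7.1.1 and the Efficacy Parameters part of the Synopsis both give description and estimation as the main focus, and both class the p-values as exploratory.

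The Efficacy Results in the Synopsis give 29.4% against 11.8% within 90 minutes and 47.1% against 23.5% within 24 hours (ITT), with 90-minute odds about three times greater under Ryanodex. ITT time to a rectal temperature of 38 °C or below is called similar, and "Overall mean cooling rates were similar in both treatment groups (ITT and mITT Analysis Sets"). In the mITT set the time to 38 °C or below was shorter with Ryanodex: median 90.0 against 103.0 minutes, and 125.0 against 195.0 minutes for 75% of subjects.

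The end of the Efficacy Results and the Conclusion then say that Ryanodex subjects "exhibited greater clinically meaningful improvement in their neurological functioning compared to SOC only-treated subjects". Both places call the difference a clinically relevant benefit and tie it to fewer complications and less long-term illness and death.

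**The concern.** The Conclusion is what most readers take away, and it is firmer than the evidence reported just before it. It omits four things that bear on how far the difference can be trusted:

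- **Design.** The trial is open-label and the endpoint is a cut-off on a clinical score. The readable text does not say whether the scorer knew the arm.
- **Size.** The result is given as percentages and an odds ratio. Neither the number of subjects behind them nor the planned interval for the difference appears in the Efficacy Results or the Conclusion.
- **Status.** The exploratory label is set out in the methods and not carried forward.
- **Temperature.** The similar ITT temperature results are listed but play no part in the Conclusion.

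The step to morbidity and mortality goes further still. It rests on an association described as known, and no readable efficacy result is a long-term outcome. A reader planning a later trial, or judging the evidence for this use, could take the benefit as demonstrated.

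**Working it through.** **Inputs.** From the Synopsis: 34 subjects analyzed, 1:1 allocation, and the ITT percentages 29.4, 47.1 and 41.2 (Ryanodex plus SOC) and 11.8 and 23.5 (SOC only). From SAP section 9.7.1.9.1: Wilson and Newcombe intervals, two-sided 95%.

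**Step 1. Counts.** Arm sizes are not printed in the readable text. Among all splits of 34, only 17 and 17 gives whole counts that match every percentage. Hence 5/17 = 29.4%, 2/17 = 11.8%, 8/17 = 47.1%, 4/17 = 23.5% and 7/17 = 41.2%.

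**Step 2. Reproduce the stated odds ratio.** With a and b responders in the two arms, OR = a(17 - b) / [b(17 - a)].

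- 90 minutes: (5 × 15) / (2 × 12) = 75/24 = 3.13, matching the stated factor of about 3.
- 24 hours: (8 × 13) / (4 × 9) = 104/36 = 2.89, matching the statement that the odds were almost unchanged.

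**Step 3. Wilson intervals at 90 minutes.** Limits are [p + z²/2n ± z√(p(1 - p)/n + z²/4n²)] / (1 + z²/n), with z = 1.96 and n = 17.

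- Ryanodex plus SOC, p = 0.2941: 0.1328 to 0.5313.
- SOC only, p = 0.1176: 0.0329 to 0.3434.

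**Step 4. Newcombe interval at 90 minutes.** The difference is d = 0.2941 - 0.1176 = 0.1765, which is three subjects.

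- Lower limit: 0.1765 - √[(0.2941 - 0.1328)² + (0.3434 - 0.1176)²] = 0.1765 - 0.2774 = -0.101.
- Upper limit: 0.1765 + √[(0.5313 - 0.2941)² + (0.1176 - 0.0329)²] = 0.1765 + 0.2519 = 0.428.

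**Step 5. Results side by side (ITT).**

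| Outcome | Ryanodex + SOC | SOC only | Difference, points (Newcombe 95% CI) | Odds ratio (Wald 95% CI) | Fisher p (exploratory) |
|---|---|---|---|---|---|
| GCS ≥ 13 by 90 min (primary) | 5/17 | 2/17 | 17.6 (-10.1 to 42.8) | 3.13 (0.51 to 19.0) | 0.40 |
| GCS ≥ 13 by 24 h | 8/17 | 4/17 | 23.5 (-8.1 to 49.6) | 2.89 (0.66 to 12.6) | 0.28 |
| GCS = 15 at 24 h | 7/17 | 4/17 | 17.6 (-13.1 to 44.4) | 2.28 (0.52 to 10.0) | 0.46 |

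All three differences favour Ryanodex, and all three intervals include zero. The gap is three subjects at 90 minutes and four for GCS ≥ 13 by 24 hours.

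**Step 6. Dependence on the cut-off.** Anyone at 15 at 24 hours has also reached 13 by then. So at least 7 of the 8 Ryanodex responders and all 4 SOC responders by 24 hours reached 15. The 24-hour difference therefore does not rest mainly on scores just at 13. The corresponding split at 90 minutes is not readable.

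**The case against.** The strongest reply is that the limits are disclosed. Open-label is in the title, the methods class the p-values as exploratory, the similar ITT temperature results are listed in the same Synopsis, and the closing sentence says only what Ryanodex may deliver. This is fair as far as it goes. It does not cover the sentences in which the improvement and the clinical benefit are stated outright, or the morbidity and mortality link. None of these disclosures puts an interval beside the claim.

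The reply can also point to supporting results: mITT odds about six times greater, shorter mITT times to 38 °C or below, and a shorter ITT duration of SOC. These stand and should not be left out. ITT is nevertheless the primary efficacy set. The mITT arm sizes are not readable, so the precision of that odds ratio cannot be checked, and duration of SOC is not a temperature measure.

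Three stronger readings are tempting, and the documents do not support them:

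- **The GCS difference is a rating artefact.** The Methodology cell is blacked out, so masked scoring cannot be excluded. Nothing readable shows bias in either direction.
- **The result hinges on the cut-off of 13 and no higher cut-off was examined.** GCS = 15 at 24 hours is reported and points the same way. SAP section 9.7.1.9.2 on sensitivity analyses is blacked out and may hold more. Nor could a higher cut-off separate rating bias from a drug effect, because an unmasked rater can favour an arm at 14 or 15 too.
- **Similar cooling disproves a neurological effect.** It does not. The ITT temperature measures fail to corroborate the GCS difference, which is a weaker statement.

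**Conclusion.** The concern holds as a matter of what the Conclusion may claim. The pre-specified analysis is not in question. The primary ITT result is a difference of three subjects, 17.6 points, with a Newcombe 95% interval from about -10 to 43. That is compatible with no difference, with a difference somewhat against Ryanodex, and with a large one in its favour. Stating a clinically relevant benefit as fact, with a link to morbidity and mortality, goes beyond this.

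The verdict rests on two assumptions. First, each arm has 17 subjects and the ITT set is all 34; the percentages and the stated odds ratio both agree with this. Second, the Synopsis is the conclusion on which readers will rely; a fuller discussion of limits in the complete study report is not among these documents. The verdict does not depend on whether GCS was scored masked, because the imprecision remains either way.

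**What to change.** Replace the benefit statement in the Conclusion, and its duplicate at the end of the Efficacy Results, with wording such as:

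> In this open-label, exploratory trial, more subjects in the Ryanodex plus SOC arm than in the SOC-only arm were recorded with a GCS score of 13 or more by 90 minutes (5/17 vs 2/17; difference 17.6 percentage points, Newcombe 95% CI -10.1 to 42.8). The interval includes no difference. In the ITT set, time to a rectal temperature of 38 °C or below and mean cooling rate were similar; in the mITT set, time to 38 °C or below was shorter with Ryanodex.

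The sponsor should confirm the counts and interval against its own tables. If GCS was scored by masked assessors, add a sentence saying so. Remove the inference to fewer complications and lower long-term morbidity and mortality, which this trial did not show, and bring the closing sentence on therapeutic benefit into line.

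No new data, analysis or table is needed, because the interval is already part of the planned primary analysis. The cost is a short text change and a less favourable conclusion.

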
Efficacy Parameters:
 
The main focus of all efficacy analyses was to describe the course of subject recovery during the study and to obtain estimates of the treatment effect. Any observed significance levels ("p-values") that were reported were to be regarded as exploratory, descriptive statistics.
 
The primary null hypothesis was that restoration of level of consciousness (defined as a return to GCS scores ≥ 13) in subjects with probable or definitive EHS was not different for subjects treated with Ryanodex in addition to immediate implementation of SOC (body cooling and supportive measures), compared to subjects treated with SOC only (body cooling and supportive measures) implemented immediately.
 
[REDACTED]
 
[REDACTED] the primary endpoint was the cumulative incidence of subjects who had achieved a GCS score ≥ 13 prior to or at 90 minutes post-randomization in the ITT analysis set. The number and percentage of subjects who achieved a GCS score ≥ 13 are presented by treatment arm. A two-sided 95% Wilson confidence interval (CI) for each treatment group proportion and a two-sided 95% Newcombe CI for the treatment difference were calculated. The odds ratio and its two-sided 95% CI were also calculated and reported. The cumulative incidence of subjects who achieved a GCS score
		

Name of Sponsor/Company: Eagle Pharmaceuticals, Inc.	Individual Study Table	(For National Authority Use only)
Name of Finished Product: Ryanodex® (dantrolene sodium) for injectable suspension		
Name of Active Ingredient: Dantrolene sodium		

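### The synopsis concludes that Ryanodex gave a clinically relevant benefit, but its primary comparison is inconclusive, and it reads two within-arm p-values as a between-arm result

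*Combined protocol and SAP*

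**What the plan says.** **Methods.** SAP section 9.7.1.9.1 and the Synopsis (Efficacy Parameters) define the primary endpoint as the cumulative incidence of GCS 13 or more by 90 minutes after randomization in the ITT set. For the comparison between arms, the Synopsis says that "a two-sided 95% Newcombe CI for the treatment difference were calculated", and then: "The odds ratio and its two-sided 95% CI were also calculated and reported". P-values "that were reported were to be regarded as exploratory, descriptive statistics". For change in GCS, the Synopsis describes a repeated-measures model whose least-squares treatment differences and 95% intervals are reported, with secondary endpoints analysed in the ITT set.

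**Results.** The ITT proportions for Ryanodex are given as "within 90 minutes (29.4%) and within 24 hours post-randomization (47.1%), compared to SOC only-treated subjects (11.8% and 23.5%, respectively". The odds of reaching the endpoint by 90 minutes "post-randomization was about 3 times greater for subjects in the SOC and Ryanodex group than for subjects who received SOC only". In the mITT set, the mean GCS change is 3.1 (p=0.017) with Ryanodex and 1.1 (p=0.179) with standard of care; percent change is 55.6% (p=0.073) and 20.2% (p=0.212). The Synopsis comments that in both cases "the within-group p-value clearly favors the SOC and Ryanodex group, compared with the SOC only group (mITT Analysis Set". No interval for any treatment difference or odds ratio is printed among the results, and no between-arm p-value.

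**Conclusion.** At the end of the efficacy results and again in the Conclusion: "The observed incremental improvement in neurologic functioning constitutes a clinically relevant benefit". The Conclusion closes with: "The results of the study provide clinical evidence of the therapeutic benefit that Ryanodex may deliver to patients with EHS".

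**The concern.** The primary analysis was built around an interval for the difference between arms, and the stated aim was to describe recovery and estimate the treatment effect. A conclusion of benefit should therefore rest on that interval. The Synopsis moves from point estimates to a stated benefit without it. With 34 of 100 planned subjects, imprecision is the main feature of the result. The shortfall is disclosed, but its consequence does not reach the conclusion.

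The p-value sentence is a separate fault of inference. Each within-arm test asks whether that arm changed from Baseline. That one arm gives a smaller p-value than the other does not test whether the arms differ. A reader of the Synopsis alone would take roughly tripled odds, a clear p-value contrast and a stated benefit as the trial's finding.

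**Working it through.** **1. Counts.** The Synopsis gives 34 analysed subjects, 1:1 allocation, and ITT percentages of 29.4, 47.1 and 41.2 (Ryanodex) and 11.8 and 23.5 (standard of care). Trying every split of 34 with 5 to 29 subjects in the Ryanodex arm, only 17/17 reproduces all five: 5/17, 8/17 and 7/17; 2/17 and 4/17. The counts are derived, not printed.

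**2. Reproducing the printed odds ratio.** At 90 minutes, (5 × 15)/(2 × 12) = 75/24 = 3.125, which agrees with the threefold odds. At 24 hours, (8 × 13)/(4 × 9) = 104/36 = 2.89, which agrees with the statement that the odds hardly changed.

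**3. Wilson interval per arm.** With z = 1.96, centre = (p + z²/2n)/(1 + z²/n) and half-width = z√[p(1−p)/n + z²/4n²]/(1 + z²/n).
- Ryanodex 5/17: 0.3321 ± 0.1993, or 13.3% to 53.1%.
- Standard of care 2/17: 0.1881 ± 0.1552, or 3.3% to 34.3%.

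**4. Newcombe interval for the difference.** d = 0.2941 − 0.1176 = 0.1765.
- Lower: d − √[(p₁−l₁)² + (u₂−p₂)²] = 0.1765 − √(0.1613² + 0.2257²) = 0.1765 − 0.2774 = −0.101.
- Upper: d + √[(u₁−p₁)² + (p₂−l₂)²] = 0.1765 + √(0.2372² + 0.0848²) = 0.1765 + 0.2519 = +0.428.

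The result is +17.6 points, 95% CI −10.1 to +42.8. With continuity correction it is −14.0 to +45.9. The documents do not say which was used.

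**5. Odds-ratio interval.** Woolf: SE = √(1/5 + 1/12 + 1/2 + 1/15) = 0.922; exp(1.139 ± 1.96 × 0.922) = 0.51 to 19.0. The conditional exact interval is 0.40 to 37.1. The method is not stated. Fisher's exact p is 0.40; the uncorrected chi-square p is 0.20.

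**6. Other ITT proportions quoted.** These uncorrected Newcombe intervals are my own; the visible text does not show them as planned output.

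| Endpoint | Counts | Difference (95% CI), points | Odds ratio (Woolf 95% CI) |
|---|---|---|---|
| GCS ≥ 13 by 24 h | 8/17 vs 4/17 | +23.5 (−8.1 to +49.6) | 2.89 (0.66 to 12.6) |
| GCS 15 at 24 h | 7/17 vs 4/17 | +17.6 (−13.1 to +44.4) | 2.28 (0.52 to 9.99) |

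**7. What the within-arm p-values imply.** This is a rough check. It assumes that they are one-sample t-tests and, as mITT arm sizes are not given, tries 4 to 17 per arm. Each SE is the mean divided by the t-value that matches its p-value; the arms are then compared by Welch's test on the difference 3.1 − 1.1 = 2.0.
- 17 per arm: SEs 3.1/2.663 = 1.164 and 1.1/1.405 = 0.783; combined √(1.164² + 0.783²) = 1.40; t = 1.43; p = 0.16.
- 4 per arm: SEs 0.643 and 0.630; combined 0.90; t = 2.22; p = 0.07.

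Over all combinations of arm sizes, p runs from 0.07 to 0.16 for change and from 0.20 to 0.29 for percent change. For percent change, even the within-arm values (0.073 and 0.212) both exceed 0.05, yet the sentence covers both measures.

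**8. Illustration only.** With standard of care held at 2/17, the uncorrected Newcombe lower limit is −10.1 at 5/17, −5.3 at 6/17, −0.5 at 7/17 and +4.5 at 8/17. This shows how far the data are from excluding no difference; it is not a planned criterion.

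**The case against.** The strongest reply is that a synopsis is a summary. The methods text says that the odds-ratio interval and the model-based differences are reported, and they may well stand in report sections that were not supplied. Nothing in the documents requires a synopsis to print intervals, and some of its text is redacted or broken off. This stands as a limit: the omission is shown for the Synopsis only. A reader might infer that the intervals were never produced or were held back; the documents do not support that.

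The Synopsis is also more candid than its conclusion suggests. It discloses 34 of 100 planned subjects, calls p-values exploratory, labels the mITT ones as within-group, and reports that cooling rates (ITT and mITT) and ITT time to 38°C or below were similar between arms. The closing sentence contains *may*, so it is wrong to call the whole conclusion unhedged. But that word does not qualify the statement of clinically relevant benefit, which appears twice, and labelling the p-values correctly does not make the contrast between them valid.

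Two further inferences are tempting. One is that the link to long-term morbidity and mortality is passed off as a trial result; its wording already marks it as outside knowledge, so any further disclaimer is editorial. The other is that the drug did not work. An interval reaching +42.8 points does not show absence of effect.

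Finally, the planned analysis itself is not at fault. The point concerns reporting and interpretation.

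**Conclusion.** The point holds for two statements in the Synopsis. First, the unqualified statement of clinically relevant benefit goes beyond the primary estimate: a difference compatible with anything from about a 10-point deficit to a 43-point gain is inconclusive. Second, the p-value sentence draws a between-arm conclusion from two within-arm tests and is invalid wherever the planned intervals are printed.

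The primary figures rest on the derived counts 5/17 and 2/17, which only one split of 34 allows. The exact limits depend on unstated choices (continuity correction; odds-ratio method), but every version includes no difference. The back-calculated between-arm p-values rest on an assumed test and assumed arm sizes and are supporting evidence only. As mITT counts are not shown, no interval is claimed for the roughly sixfold mITT odds.

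**What to change.** 1. Print the planned primary Newcombe interval and the odds-ratio interval beside the 90-minute percentages and the threefold odds, and state the variant used for each.
2. Delete the sentence that compares within-group p-values, or replace it with the between-arm difference in GCS change and its 95% interval, naming the analysis set. The model described in the Synopsis gives such a difference for the ITT set.
3. Restate the efficacy conclusion wherever the benefit statement appears, for example: *Point estimates favoured Ryanodex, but the primary interval includes no difference; with 34 of 100 planned subjects the result is inconclusive and hypothesis-generating.*

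The cost is wording only. By the documents' own account the primary intervals and the ITT model estimates already exist; an mITT between-arm estimate might need a short calculation on existing data. No data collection, endpoint or analysis set changes. The downside for the sponsor is a less favourable conclusion.
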